9.3.3 Subject Identification

Subject study identification numbers will be assigned at the Screening Visit. Subject numbers will be consecutive at each study site beginning with 001. Site numbering will begin at the number 201. Subject identification will consist of the site number (3 digits) followed by the subject number (3 digits), e.g., the first subject at Site 201 would be 201001 and the fifth subject at Site 235 would be 235005. Subject numbers will be consecutive at each study site beginning with 001. Subject identification numbers will be used throughout the trial.

9.4 Study Treatment

9.4.1 Identity of Investigational Products

The investigational products are manufactured by Haupt Pharma, Munster, Germany, in accordance with applicable current Good Manufacturing Practice (GMP).

Dosage form description	24 pink tablets containing 15 mg E4/3 mg DRSP 4 white placebo tablets
Package description	Blister pack (PVC/Aluminum) containing 28 tablets (24 pink and 4 white tablets)
Dose per time unit	1 tablet daily
Dispensing	 Dispense the blister as follows per subject: 4 blisters on Visit 2 and then 3 blisters on Visits 4 (Cycle 4), 5 (Cycle 7) and 6 (Cycle 10). 1 spare blister on Visit 2 and, if necessary, on Visit 4, 5 and/or 6.

The following investigational products will be administered:

9.4.1.1 Labeling

The investigational product will be labeled according to regulations and local requirements and will contain at minimum the following information:

- Drug name or number/code
- Protocol number
- Blister content (24 pink tablets containing 15 mg E4/3 mg DRSP and 4 white placebo tablets)
- Lot number
- Expiry date
- For oral administration
- Storage conditions
- Caution: New Drug Limited by Federal (or United States) law to investigational use.
- Treatment number
- Manufacturer's name and address
- Keep out of reach of children

9.4.1.2 Storage and Drug Accountability

The Investigator will be responsible for the suitable storage of the investigational product in compliance with the storage instructions and must restrict access to the study personnel only. Under no circumstances will the Investigator allow the investigational products to be used other than as directed by this protocol. The investigational product must be protected from unauthorized access (e.g. in a locked storage facility). Appropriate storage conditions at the site must be ensured either by controlled room temperature or by completion of a temperature log in accordance with local requirements and storage instructions on a regular basis, showing minimum and maximum temperatures reached over the time interval. The Principal Investigator will have overall responsibility for the use of the investigational product at the site. The Principal Investigator or Designee will confirm receipt of the investigational product and will verify the contents of the shipment, using an interactive web response system (IWRS) upon receipt of the product. The Investigator or Designee shall maintain accurate investigational product inventory records, including the quantities and date of receipt of supplies from the Sponsor, and the quantities and dates of dispensing to each study subject. Shipping and handling of all investigational products will be conform to ICH-GCP guidelines, GMP and Local regulatory guidelines.

At Visits 3, 4, 5, and 6, the Investigator should collect the investigational product (unused and empty) including spare blister if used (even if partially used) of the completed treatment cycles for drug accountability. Unused spare blister will be left for the subject. Used spare blisters will be replaced by a new spare blister. At Visit 7, the Investigator should collect all unused investigational product including spare blister (used or not), empty blisters for final drug accountability.

At completion of the study, to satisfy regulatory requirements regarding drug accountability, all investigational products will be stored, inventoried, reconciled, and destroyed or returned to the Sponsor according to applicable regulations. A written explanation must be provided for any discrepancies. The study monitor must review all records of drug accountability prior to the return or destruction of any supplies.

This drug accountability log must be available for inspection during an audit (e.g., by Sponsor or a regulatory agency). At the conclusion of the study, the Investigator must provide a copy of this record to the Sponsor.

9.4.2 Method of Assigning Subjects to Treatment

This is a 1-treatment arm open-label study. The subject will undergo screening where pretreatment clinical evaluations and specific procedures will be completed at the Screening Visit. Authorized site personnel will acknowledge that the subject met all of the specified inclusion criteria and none of the exclusion criteria before subject enrolment.

At enrollment visit, after IWRS contact, investigational product packs labeled with study information will be assigned to the subject.

9.4.3 Treatment Compliance

Treatment compliance for the investigational product will be assessed based on the response values entered by the subject in the diary on a daily basis (see Section 9.6.1). A comparison will be made between the number of tablets expected to be used, based on the total number of treatment days, and the number of tablets taken according to the subject's diary.

In addition, the data will be used to identify when a pill has been missed.

At each visit, the diary entries will be compared to the returned tablets to ensure consistency but the diary data will be used for compliance assessment. In case of discrepancy between the diary data and the returned tablets, the investigator will discuss with the subject and document this in the source data.

9.4.4 Selection of Doses and Timing of Administration in the Study

The daily dose used in this study, i.e. 15 mg E4 and 3 mg DRSP, has been selected on the basis of the data generated during the Phase 2 program. It was associated with a high inhibition of ovarian function, no ovulation, a good safety profile, and the most favorable bleeding pattern/cycle control observed among the different E4 combinations that were evaluated (see Section 7.2).

The investigational product is administered once daily following a 24/4-day regimen, i.e. one 15 mg E4/3 mg DRSP active tablet per day for 24 consecutive days followed by one placebo tablet per day for 4 consecutive days.

This 28-day cyclic regimen must be taken for up to 13 consecutive cycles. The treatment must be taken once daily at approximately the same time of the day.

9.4.4.1 Instructions for starting the first pack of tablets

- Women who did not use any contraceptive method or who used a barrier contraceptive method will be instructed to begin the investigational product on the first day of the next menstrual bleeding. Starting on Days 2-5 is also allowed, but a condom must be used until the subject has completed 7 days of uninterrupted active tablet intake. If the menstrual cycle prior to start of first pack of tablets is shorter than 21 days or longer than 35 days, the subject should not start the investigational product and will be withdrawn from the study (section 13.4). The subject should contact the study staff as soon as possible to schedule an Early Termination Visit (section 9.5.4) and to discuss an alternative contraception to use (section 9.6.4.9).
- Women switching from another COC or progestin-only pill will start the investigational product at the time when the next pill pack of the previous pill would have been due.
- Women switching from a hormonal vaginal ring or transdermal patch will start the investigational product when the next application would have been due.

Amendment Final Version 1.1

• Women switching from an injectable hormonal method of contraception will start the investigational product on the first day of spontaneous menstrual bleeding following an interval after the last injection, which can vary depending of the form:

EST*w***TRA**

- 10 months after the injection of a product with a 3-month duration;
- 6 months after the injection of a product with a 2-month duration;
- 3 months after the injection of a product with a 1-month duration.

Starting on Days 2-5 is also allowed, but a condom must be used until the subject has completed 7 days of uninterrupted active tablet intake.

• Women switching from an intrauterine or dermally implantable contraceptive will start the investigational product on the day of removal. A condom must be used until the subject has completed 7 days of uninterrupted active tablet intake.

The first day of the first pink tablet intake after enrollment is Day 1. The subject places one of the 7 self-adhesive day label strips that corresponds to her Day 1 starting day onto the card of the blister to indicate the day she started. The study staff will show the subject how to fix the first label.

She then starts taking one tablet daily, at approximately the same time of the day, beginning with the first pink tablet in the top row. The subject completes her 28-tablet regimen when she has taken the last tablet in the blister pack.

9.4.4.2 Dosing Instructions

Each time investigational product is dispensed to the subject, site personnel will instruct the subject as follows:

- Take one pink tablet every day for 24 consecutive days (Day 1 through Day 24), followed by one white placebo tablet every day for 4 consecutive days (Day 25 through Day 28).
- When the pack of tablets is empty, start the next pack on the next day after the last white tablet of the previous pack has been taken. When starting a new pack of tablets, take the first pink tablet of the pack. There should be no interruption between two blister packs.
- Take the investigational product at approximately the same time each day throughout the study. The time of day should be determined by the subject.
- Return all blister packs to site personnel at the following visit.

9.4.4.3 Instructions in case of missed tablet(s) or in conditions potentially reducing the contraceptive efficacy

If the subject has vomiting or diarrhea within 4 hours of tablet intake, she should take another tablet from the extra pack (spare blister) as a replacement.

If the subject inadvertently misses one or more of the tablets, the following instructions must be followed⁶:

- If one active pink tablet is late (< 24 hours since a tablet should have been taken) or if one active pink tablet has been missed (24 to < 48 hours since a tablet should have been taken):
 - Take the late or missed active pink tablet as soon as possible.
 - Continue taking the remaining active pink tablets at the usual time (even if it means taking two active pink tablets on the same day).
 - Use of condom is not required.
- If two or more consecutive active pink tablets have been missed (\geq 48 hours since a tablet should have been taken):
 - If between Day 1 & Day 17:
 - Take the most recent missed active pink tablet as soon as possible (any other missed tablets should be discarded).
 - Continue taking the remaining active pink tablets at the usual time (even if it means taking two tablets on the same day).
 - Use condom or avoid sexual intercourse until 7 days of uninterrupted active pink tablet intake.
 - Consider emergency contraception as per current practice if the woman had unprotected intercourse during the missed pill interval.
 - If between Day 18 & Day 24:
 - Omit the hormone-free interval by finishing the active pink tablets in the current pack and starting a new pack the next day.
 - If unable to start a new pack immediately, use condoms or avoid sexual intercourse until 7 days of uninterrupted active pink tablet intake from the new pack.
 - If this occurs during the last cycle, the subject should contact the study staff to know what she has to do with the next contraception.

If the subject inadvertently misses any of the white placebo tablets:

- Skip the missed white placebo tablet(s) and the remaining tablets are taken at the regular time.
- Use of condoms is not required during this time.

Amendment Final Version 1.1

Anytime a subsequent cycle of the product/pack is started later than the day following administration of the last white tablet, the subject should use condoms until she has taken pink tablets daily for 7 consecutive days.

9.4.4.4 In case of short-term intake of drugs that may decrease the efficacy of the COC

Subject is allowed to take drugs potentially decreasing the efficacy of the COC for a maximal period of 10 consecutive days (for example, CYP 3A4 inducers). Subjects must be instructed to use condoms when these drugs are used and during 7 days of uninterrupted pink tablet intake after finishing the medication.

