- 4. The subject does not receive unauthorized concomitant medication (see section 9.4.6.1 of the protocol) for at least one day during the cycle
- 5. The subject does not miss 4 or more days of active pills during the cycle
- 6. The subject does not miss 2 or more consecutive days of active pills during the cycle
- 7. The length of the previous cycle is not longer than 28 days
- 8. The subject had no adverse events of vomiting and/or diarrhea during the cycle

In the second of these definitions, cycles qualify if they meet all of the criteria 1 and 3 to 8 listed above (i.e. occurrence of sexual intercourse is not taken into account),

The following rules will be applied to all types of exposure:

- If conception occurs in a cycle, then that cycle will be included in the denominator, regardless of whether or not other methods of birth control were used during that cycle, or whether or not sexual intercourse was confirmed.
 - If the conception is confirmed to be during a specific cycle in the narrative and this cycle is not in the diary data, then the cycle will be included in the denominator, regardless of whether or not other methods of birth control were used during that cycle, or whether or not sexual intercourse was confirmed
 - The only exception is for user failure pregnancies, which will be excluded from the exposure definitions based on the compliance rules 3 to 8 above, since they do not meet criterion 3
- Cycles after the cycle of conception will be excluded from the denominator
- Missing data from the diary will be handled according to section 5.15.1.

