5.9.4 Method and User Failure Pregnancies

User failure pregnancies are pregnancies where the subject did not take the study medication correctly as per Section 9.4.4 of the Protocol during the cycle in which the estimated date of conception occurred or used drugs that have the potential to trigger interactions with COC (Section 9.4.6 of the Protocol). Pregnancies not identified as due to user failure will be considered to be method failure pregnancies. The pregnancy narratives from the Principal Investigator are used to determine whether a pregnancy is a user or method failure pregnancy.

Each on-treatment pregnancy will be reviewed in conjunction with the data collected and classified as either a method failure or a user failure pregnancy prior to database lock.

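### Protocol 9.4.4.3 gives conflicting back-up instructions for a pack started one day late, and the SAP's method/user failure label refers back to that text

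*Protocol*

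**What the plan says.** **Protocol 9.4.4.3, missed pink tablets.** The first bullet covers a late tablet and the case "if one active pink tablet has been missed (24 to < 48 hours since a tablet should have been taken". Its back-up instruction is "Use of condom is not required". The bullet has no day limit. The next bullet, for two or more missed tablets, opens its first branch with "If between Day 1 & Day 17", so the missed-tablet rules reach the first tablet of a pack.

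**Protocol 9.4.4.3, missed white tablets.** "Skip the missed white placebo tablet(s) and the remaining tablets are taken at the regular time", followed by "Use of condoms is not required during this time".

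**Protocol 9.4.4.3, closing paragraph.** "Anytime a subsequent cycle of the product/pack is started later than the day following administration of the last white tablet, the subject should use condoms", and this lasts until pink tablets have been taken on seven days in a row. No minimum delay is given, and nothing says whether this sentence or the missed-tablet bullet prevails.

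**Failure label.** SAP 5.9.4 calls a pregnancy a user failure when a woman "did not take the study medication correctly as per Section 9.4.4 of the Protocol during the cycle in which the estimated date of conception occurred"; use of interacting drugs also counts. Protocol 12.4 counts the missed-pill instructions as part of correct use. Both documents have each on-treatment pregnancy classified before database lock.

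**Cycle accounting.** SAP 5.7.1 counts days between Day 28 and the next pack as missed pills of the earlier cycle. For the compliance-restricted method failure denominators, criterion 7 in SAP 5.1.1 requires that "The length of the previous cycle is not longer than 28 days". Protocol 9.4.6.2 and 12.4 remove cycles with condom use from the Pearl Index denominator, but a conception cycle always counts.

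**The concern.** Starting a pack one day late is a foreseeable event in a 13-pack study, and the protocol answers it twice, differently. Women and sites could be given either advice.

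The statistical stake is mainly the method failure Pearl Index, a named secondary endpoint. A woman who starts one day late, uses no condom and conceives has followed the bullet and not followed the closing paragraph. The SAP sends the label back to the section that contains both. The label is assigned in an open-label study, after the pregnancy is known and from the investigator's narrative, so the rule should be fixed in advance.

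A second, smaller stake is the denominator. If the advice changes whether women use condoms, it changes which cycles count.

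**Working it through.** **1. The rules applied to each event**

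| Event | Missed-tablet or placebo rule | Late-pack sentence | Result |
|---|---|---|---|
| First pink tablet of packs 2–13 taken 24 to <48 h late | No condom required | Condoms, 7 days of pink tablets | Conflict |
| Same tablet, 48 h or more late (two or more missed) | Condom or abstinence, 7 days | Condoms, 7 days | Broadly agree |
| Day 28 white tablet skipped, next pack on schedule | No condom | Last white tablet administered was Day 27, so Day 29 is literally late | Wording mismatch |
| Day 25, 26 or 27 skipped, Day 28 taken, next pack on schedule | No condom | Not triggered | No conflict |

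The conflict is confined to the first row. The third row is a defect in the trigger wording.

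**2. The failure label after a one-day-late start without condoms**

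- Under the bullet, the missed-pill instructions were followed: method failure.
- Under the closing paragraph, they were not: user failure.
- SAP 5.7.1's example has start dates of 1 February and 3 March and books both gap days to Cycle 1. By the same rule, a one-day-late start puts one missed pill in the previous cycle, which then lasts 29 days. The conception cycle itself may show no missed pill, although SAP 5.9.4 looks at that cycle.
- Criterion 7 nevertheless treats the late-started cycle as non-compliant.

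**3. Which quantities can move**

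- Primary numerator: no. All on-treatment pregnancies count.
- Primary and modified at-risk denominators: only through condom use recorded in the diary, and only in non-conception cycles.
- All-cycles denominator: no. It ignores condoms.
- Compliance-restricted denominators: criterion 7 already excludes a late-started non-conception cycle, whatever the back-up use.
- Method failure numerator: yes, through the label.

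**4. Size**

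The plan's own figure comes first. With the exact Poisson upper limit ½χ²(0.975; 2(x+1)), x = 14 gives 23.490. The difference is 9.4896, and 9.4896 × 1300 = 12,336.5, which rounds up to the stated 12,337 cycles. Power there is 0.940; at 12,336 it is 0.899. The figure reproduces.

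Planned at-risk cycles (Protocol 12.1: 1800 subjects, 45% dropout with 4 cycles each, 13 cycles per completer, 20% not at risk):

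1800 × (0.55 × 13 + 0.45 × 4) × 0.8 = 1800 × 8.95 × 0.8 = 12,888.

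Effect of relabelling one pregnancy: 1300/12,888 = 0.101; 1300/12,337 = 0.105.

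Cycles that follow a pack change: 12,888 − 1800 × 0.8 = 12,888 − 1,440 = 11,448. The documents give no rate of late starts. If 1% to 5% of packs started one day late (assumption), that is 114 to 572 cycles, or 0.9% to 4.4% of 12,888.

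Expected pregnancies in those cycles, at a Pearl Index of 1.0 and average risk (assumption): 12,888/1300 = 9.9; times 0.9% to 4.4% gives 0.09 to 0.44. The expected shift is then about 0.01 to 0.04.

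Upper bound on lost exposure, if every such cycle dropped out through condom use: 12,888 − 114 = 12,774 to 12,888 − 572 = 12,316. The lower figure is 21 cycles short of 12,337. It lies between 12,300 (power 0.9005) and 12,336 (0.8988), so power is still about 0.90.

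**The case against.** **The two sentences can be harmonised.** The bullet says a condom is not required, which does not forbid one, so a woman who uses condoms satisfies both. The closing sentence is the one written for late packs, while the bullet tells her to carry on with the remaining tablets of a pack in use. The SAP also handles late starts separately, through criterion 7. This is a natural reading, but neither document states it. A woman who uses no condom satisfies only one sentence, and that is the case in which the label matters.

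**The label may concern tablet intake only.** SAP 5.9.4 speaks of taking medication correctly, and Protocol 9.4.4.2 asks for no interruption between packs, so any late start could count as incorrect use. That would favour user failure. But Protocol 12.4 brings the missed-pill instructions into correct use, and SAP 5.7.1 puts the gap in the cycle before conception. Pre-lock review of each case helps, but it does not supply the missing rule.

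**Stronger readings that the documents do not support.** A reader might infer that at-risk status depends on which sentence the site applies. It does not: it is set by what the diary records, under one fixed rule. A reader might also infer that any skipped white tablet makes an on-time pack late. Only a skipped Day 28 tablet does so, and the placebo rule's exemption may be meant for the placebo days alone. Both objections stand, and they limit the point.

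**Conclusion.** The conflict is real and confined to a first pink tablet of packs 2 to 13 taken one day late. It leaves the method/user failure label undetermined for a conception after such a start without condoms. Each such pregnancy is worth about 0.10 on the method failure Pearl Index, roughly a tenth of the assumed overall index of 1.0.

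That figure is the effect of one moved pregnancy and should not be read as the expected shift, which is about 0.01 to 0.04 if 1% to 5% of packs start late and those cycles carry average risk. Both conditions are assumptions.

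A reader might conclude that the primary Pearl Index is misclassified or the sample size wrong. Neither follows. The primary numerator and conception cycles are unaffected, the denominator moves only with recorded condom use, and 12,337 reproduces. The Day 28 mismatch is a secondary wording point.

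**What to change.** 1. **Protocol 9.4.4.3.** The missed-pink-tablet bullet and the closing late-pack paragraph must be reconciled so that one instruction applies to a one-day-late start. The late-pack trigger must also be reconciled with the placebo rule for a skipped Day 28 tablet. The content is for the sponsor's clinicians; no view is taken here on which instruction is right.
2. **SAP 5.9.4.** State before database lock how a conception after a one-day-late pack start is labelled under the reconciled text, including whether a gap day booked to the previous cycle counts against the conception cycle.
3. **SAP 9.5.2.2.** Add one sensitivity row showing the method failure Pearl Index with such conceptions classed each way.

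The cost is a short protocol clarification with updated subject instructions, one SAP sentence and one table row. No subjects or procedures are added, and the SAP items also work for data collected under the present text.

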 - CYP 3A4 inhibitors: azole antifungals, phenylbutazone, modafinil, cimetidine, verapamil, macrolides, diltiazem and grapefruit juice.
 - HIV/HCV protease inhibitors and non-nucleoside reverse transcriptase inhibitors.

These drugs or herbal products may decrease the effectiveness of hormonal contraceptives or increase breakthrough bleeding. Subjects must be instructed to use a back-up contraceptive method when these drugs are used, up to and

including the next 7 days after finishing the concomitant therapy and to record this back-up contraception in the subject diary (see Section 9.6.1). It is the responsibility of the Investigator to ensure that any change in concomitant medications during the study is recorded in the source documentation and entered in the electronic case report form (eCRF).

Warning: oral contraceptives may interfere with the metabolism of other drugs. Accordingly, plasma and tissue concentrations may be affected (e.g. cyclosporine). Consult the prescribing information of concomitant drugs for possible interactions with oral contraceptives.

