9.4.6.2 Condoms and other contraceptive methods

Use of condoms is allowed during the course of the study only to avoid transmission of STIs or in case of missed tablet(s) or unauthorized concomitant therapies. Condom use must be recorded in the subject diary. Use of any other contraceptive methods must also be recorded in the subject diary (see Section 9.6.1). The cycles during which condom(s) or other contraceptive method(s) than the investigational product were used will be excluded from the Pearl Index calculation.

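### Protocol 9.4.4.4 and 9.4.6.1 set different back-up periods after a short course of an interacting drug, and under 9.4.6.1 back-up can end after only 3 active tablets

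*Protocol*

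**What the plan says.** Protocol 9.4.4.4 allows drugs that may lower the efficacy of the pill for at most 10 consecutive days and gives CYP 3A4 inducers as its example. It says "Subjects must be instructed to use condoms when these drugs are used" and continues the requirement "during 7 days of uninterrupted pink tablet intake after finishing the medication". Pink tablets are the active ones, so this rule counts active tablets.

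Protocol 9.4.6.1 lists CYP 3A4 inducers, CYP 3A4 inhibitors and HIV/HCV drugs as unauthorized concomitant therapies. It then requires an unspecified back-up method during use, up to and "including the next 7 days after finishing the concomitant therapy". This rule counts days and does not mention which tablets are taken on them.

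Other back-up instructions in 9.4.4 count active tablets:

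- First pack started on Days 2-5 (9.4.4.1): "a condom must be used until the subject has completed 7 days of uninterrupted active tablet intake". The same wording applies after removal of an intrauterine or implanted method.
- Two or more active tablets missed on Days 1-17 (9.4.4.3): "Use condom or avoid sexual intercourse until 7 days of uninterrupted active pink tablet intake".
- New pack started late (9.4.4.3): "the subject should use condoms until she has taken pink tablets daily for 7 consecutive days".

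Protocol 9.4.6.2 deals with the denominator: cycles in which condoms or methods other "than the investigational product were used will be excluded from the Pearl Index calculation".

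**The concern.** A woman on a short course of an inducer falls under both sections. Each says that she must be instructed, neither cites the other, and nothing says which prevails. How long she is told to use condoms therefore depends on which section the site reads.

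The shorter rule is the exception in the plan. The stake is an instruction meant to prevent unintended pregnancy in women taking an investigational contraceptive. A site that follows 9.4.6.1 as written can end back-up before the woman has taken the 7 uninterrupted active tablets that 9.4.4.4 asks for.

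**Working it through.** The documents give no figure for this point, so the check is a day count.

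**Inputs.** Active tablets on Days 1-24 and placebo on Days 25-28 (9.4.4.2); the two back-up rules (9.4.4.4 and 9.4.6.1). Tablets are assumed to be taken daily, with the next pack starting on the day numbered 29 here.

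**Formulas.** Let the drug end on Day *d*.

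- 9.4.6.1: back-up ends on Day *d* + 7.
- 9.4.4.4, if placebo days break the run: back-up ends on Day *d* + 7 for *d* ≤ 17, and on Day 35 (the seventh active tablet of the next pack) for *d* = 18 to 28.
- 9.4.4.4, if placebo days only pause the run: back-up ends on the day of the seventh active tablet after the drug.

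**Results.** For *d* = 1 to 17 all three give *d* + 7, with 7 active tablets in the window. For later end days:

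| Drug ends, Day *d* | Active tablets on Days *d*+1 to *d*+7 | 9.4.6.1 stop | 9.4.4.4 stop, run broken | 9.4.4.4 stop, run paused | 9.4.6.1 shorter by (broken / paused) |
|---|---|---|---|---|---|
| 18 | 6 | 25 | 35 | 29 | 10 / 4 |
| 19 | 5 | 26 | 35 | 30 | 9 / 4 |
| 20 | 4 | 27 | 35 | 31 | 8 / 4 |
| 21 | 3 | 28 | 35 | 32 | 7 / 4 |
| 22 | 3 | 29 | 35 | 33 | 6 / 4 |
| 23 | 3 | 30 | 35 | 34 | 5 / 4 |
| 24 | 3 | 31 | 35 | 35 | 4 / 4 |
| 25 | 4 | 32 | 35 | 35 | 3 / 3 |
| 26 | 5 | 33 | 35 | 35 | 2 / 2 |
| 27 | 6 | 34 | 35 | 35 | 1 / 1 |
| 28 | 7 | 35 | 35 | 35 | 0 / 0 |

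Three ranges matter:

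- The rules differ for end Days 18-27, which is 10 of the 28 possible end days.
- The minimum of 3 active tablets occurs for end Days 21-24.
- For end Days 18-21, back-up under 9.4.6.1 is over by Day 28, before the next pack begins.

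**Effect of the longer rule on at-risk cycles.** The cycle in which the drug ends already contains condom use. The longer rule excludes one further cycle only if 9.4.6.1 would have stopped by Day 28 and 9.4.4.4 runs past it. That is *d* = 18 to 21, or 4 of 28 end days, on either reading.

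From the assumptions in Protocol 12.1, expected at-risk cycles are 1800 × (0.55 × 13 + 0.45 × 4) × 0.80 = 1800 × 8.95 × 0.80 = 12,888. The plan requires 12,337, so the margin is 12,888 − 12,337 = 551 cycles. If end days are spread evenly over the pack (an assumption), using up that margin would take 551 ÷ (4/28) = 3,857 courses. That is 3,857 ÷ 1800 ≈ 2.1 per woman.

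**The case against.** The strongest reply is that the sections can be read together. Neither sentence forbids longer use, 9.4.4.4 is the more specific one, and a site that follows it also satisfies 9.4.6.1. On that view only a cross-reference is missing. This does not remove the problem: a site that follows 9.4.6.1 as written also believes it is compliant, and it gives the shorter period.

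A second reply is that the comparison with late starts and missed tablets is imperfect, because in those cases active tablets were not taken, whereas a woman on an interacting drug keeps taking them. For two or more tablets missed on Days 18-24, 9.4.4.3 tells her to omit the placebo interval and does not ask for condoms routinely. That is a fair limit on the analogy. But where 9.4.4.3 does ask for condoms in that window, because the new pack cannot be started at once, it again counts 7 days of active tablets.

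Some limits stand in full. The woman continues the study pill, so what ends is the back-up requirement, not all protection. The documents do not show that 3 active tablets are inadequate; 9.4.4.4 is used as the standard because the plan itself sets it. Exposure is also restricted: regular users of these drugs are excluded, the drugs are otherwise unauthorized, and permitted courses last at most 10 days.

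**Conclusion.** The concern holds. The protocol gives two different mandatory back-up instructions for the same situation, and the 9.4.6.1 version is shorter for a drug ending on Days 18-27. The shortfall is 1-10 days if placebo tablets break the run and 1-4 days if they pause it. The window contains as few as 3 active tablets instead of 7. For the other 18 of 28 end days the rules agree.

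These counts assume daily tablet intake and no gap between packs. The documents give no frequency of such courses, so no number of affected women can be stated. No claim is made about the primary Pearl Index numerator or the user-failure classification. The point should be corrected because it concerns protection of participants and the remedy is simple.

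**What to change.** In Protocol 9.4.6.1, replace the 7-day wording with the 9.4.4.4 rule: condoms during drug use and until 7 days of uninterrupted active tablets have been taken afterwards. A cross-reference to 9.4.4.4 would also do, provided it covers every drug listed in 9.4.6.1, since 9.4.4.4 gives only inducers as its example. Naming condoms would match 9.4.6.2. State in 9.4.4.4 whether placebo days break or pause the run; for a drug ending on Day 18 the two readings differ by 6 days (Day 35 against Day 29). Either reading secures 7 active tablets.

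The text change is about one line plus a note to sites. As a protocol change it needs the reviews and approvals set out in Protocol 13.2. No SAP change is needed. The cost to the analysis is at most one extra excluded cycle per course, and only for courses ending on Days 18-21, which is small against the planned margin of 551 at-risk cycles.
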